Each of these responses has a score between 0 and 4 (some are reverse scored), meaning each question has a score between 0 and 4. The clinical score is calculated by multiplying the total mean score (total of all item scores divided by number of items completed) by 10. However, because the YP-CORE has 10 items, this calculation is identical to simply adding the raw score of all 10 items, providing all 10 items have been completed. This gives a simpler and quicker way for practitioners to arrive at the clinical score. The clinical score is the total out of 40.

Figure 6: YP-CORE scale

### OVER THE LAST WEEK.....

|   | Not at all                 | Only occasionally          | Sometimes                  | Often                      | Most or all of the time    |
|---|----------------------------|----------------------------|----------------------------|----------------------------|----------------------------|
| 1. I've felt edgy or nervous                        |  0 |  1 |  2 |  3 |  4 |
| 2. I haven't felt like talking to anyone            |  0 |  1 |  2 |  3 |  4 |
| 3. I've felt able to cope when things go wrong      |  4 |  3 |  2 |  1 |  0 |
| 4. I've thought of hurting myself                   |  0 |  1 |  2 |  3 |  4 |
| 5. There's been someone I felt able to ask for help |  4 |  3 |  2 |  1 |  0 |
| 6. My thoughts and feelings distressed me           |  0 |  1 |  2 |  3 |  4 |
| 7. My problems have felt too much for me            |  0 |  1 |  2 |  3 |  4 |

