## Analysis of Harms

There is a high level of heterogeneity of interventions and measures when it comes to therapeutic intervention with unaccompanied asylum seeking children, however, evidence suggests positive impacts of such interventions (Children's Society, 2018). However, there is some evidence that therapy can have harmful consequences. The Experiences and Needs of Refugee and Asylum Seeking Children in the UK Literature Review (2005) discusses the possibility of pathologising and stigmatisation of young people's as possible harmful impact of therapy. Furthermore, there are numerous sources of qualitative evidence on negative experiences of therapy, which can be potentially harmful. The findings from Curran et al. suggest that "Contextual issues, such as lack of cultural validity and therapy options together with unmet client expectations fed into negative therapeutic processes (e.g., unresolved alliance ruptures). These involved a range of unhelpful therapist behaviors (e.g., rigidity, over-control, lack of knowledge) associated with clients feeling disempowered, silenced, or devalued". This remains an under-researched area using quantitative methods.

Unintended consequences of the intervention, including harms, will be explored in the IPE. Given the positive evidence around therapeutic intervention, it is not thought that My View would inflict undue harm. Some of the issues raised above will be mitigated by appropriate eligibility and assessment processes to ensure My View is appropriate for the young people, careful selection and matching of therapists and therapies for young people, and the development of the therapeutic relationship and coping skills.

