# Implementation and Process Evaluation

## Aims

The implementation and process evaluation (IPE) aims both to answer distinct IPE questions and to create understanding around implementation outcomes that are useful for complementing and understanding the findings from the RCT impact evaluation. This knowledge is important for understanding the programme, its implementation in this evaluation, and creating knowledge for a potential scale up of the programme. As such, the key research questions addressed by the IPE will focus on the implementation outcomes that are a precursor to positive intervention effects and appropriate to understanding 'My View' intervention which is still developing and being refined. These research questions build upon the pilot evaluation published by the British Refugee Council, for example by looking at the appropriateness and fit of the programme, acceptability, and cultural barriers to engagement. At the same time, the research questions also acknowledge the importance of revisiting and specifying the current intervention further, including understanding the mechanisms for change, specifying the intervention activities that have taken place, and examining new elements such as the online delivery.

Critical in the IPE data collection activities will be the understanding of the context of mental health for UASC and the context of delivery for partners. Although we are specifying our plans here, we will be flexible to the needs of delivery of the intervention and the needs of the populations served by the intervention, and we may modify sample sizes and data collection activities accordingly (e.g., for example, by allowing flexibility in the interview and bringing in more arts-based methods rather than semi-structured interviews or by not recruiting young people with particularly vulnerable mental health at the end of the intervention).

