## Design

Table 5 below provides an overview of the indicator, output, or frame of analysis for each research question and how we intend to collect this data.

Table 5: IPE design table

| IPE Design Table  |  |
|---|--|
| Indicators, output, or analysis   | Method   |
| 1. Mechanisms of change: What are the perceived mechanisms of change for 'My View' to achieve the intended outcomes for young people?  |  |
| 
 
● Logic model diagram
 
● Perceived changes in service and client outcomes including unintended consequences and risks of harm               
 
○ Perceived changes in services and access to services (e.g. access to education and housing, timeliness in services)
 
○ Perceived impacts on young people (e.g., symptomatology, negative peer influences)
 
 
 
  | 
 
● Logic model workshops
 
● Interviews with staff
 
● Interviews with young people
 
 |
| 2. Adoption: What is the programme reach? How many took up the service? What kinds of activities did they do, and what referrals were made and followed upon?  |  |
| 
 
● Number of referrals
 
● Number of eligible referrals
 
● Numbers taking up               
 
○ One-to-one therapy
 
○ Group therapy
 
 
 
● Number of sessions completed within the 12 weeks 'treatment period'               
 
○ Mean, median, mode
 
○ Percentage reaching threshold of 'treated'
 
 
 
● Description of services and activities undertaken
 
● Number of young people who were overridden allocation from the RCT
 
● Justifications for overriding RCT allocation
 
● Number and types of onwards referrals made               
 
○ Any data on referrals accepted
 
 
 
 | 
 
● Individual-level administrative data – Records by the British Refugee Council
 
                  |
| 3. Acceptability: How acceptable do participants and staff find 'My View' (e.g., content, comfort, number of sessions, online nature)? Is it viewed as an improvement on services as usual by young people, delivery partners, and social workers? What adaptations have   |  |

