## Methods

### Sample and Recruitment

Administrative data will be pseudonymised individual-level data and aim to comprehensively cover all referrals and participants and will be shared with appropriate data protection safeguards, data protection impact assessments, and using data sharing agreements.

Interview participants will be purposively sampled across the four geographic sites and remote delivery per the target numbers below under data collection. We will recruit by providing information sheets through the British Refugee Council for interviews via an opt-in basis. We will provide information on the evaluation in the training for British Refugee Council and provide support for recruitment throughout the evaluation. For adult stakeholders, we may also recruit through networks and publicly available contact information.

Interviews with children and young people after completion of the programme, so as not to interfere with counselling or intervention outcomes (n=40), with purposive sampling across the 4 sites and amongst participants who completed the 1:1 session, who did group sessions, who had crisis support, and a few who were offered the programme but decided not to participate. The exact sampling frame will be decided in consultation with the programme when distribution of participants and their demographics are better understood. We will not aim for a representative sample, but we will aim to sample purposively for a diversity of experiences and information, while ensuring that participation is entirely voluntary and that there is understanding in order to be able to consent to participation. Information sheets and consent forms will be translated into appropriate languages. We plan to compensate participants £20 for 1-hour of their time for interviews and to provide interpreters and translation of information and consent sheets where appropriate.

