## Risks

Table 7: Risk register

| Risk   | Mitigation  |
|--|---|
| Low participation by young people in My View   | The programme has and will mitigate against this (e.g., understanding cultural competency, well-connected, integrated into existing services). The evaluation will examine adoption and acceptability, including the programme reach and take up as well as the acceptability by participants and staff.
Likelihood: Medium
Impact: High  |
| Difficulty in recruiting young people participants of for interviews   | We are ensuring that the info sheet is translated, and interviews are short and concise.
We are also offering small compensation/ incentives for interviews, and only recruiting for interviews after counselling completion when there will be better trust built up
Likelihood: Low
Impact: Medium   |
| Staff and young people only want to report positive aspects of the service in IPE evaluation   | We will mitigate this through: 
 
● Independence of the evaluation team
 
● Careful discussion of consent processes and anonymity and confidentiality
 
● Use of interpreters where necessary
 
● Use of open questions, probes in semi-structured interviews
 
 Sensitively approaching data collection
Likelihood: High
Impact: Medium |
| Difficulties in carrying out My View as designed and planned by programme team (e.g., staff illness/turnover, Covid-19 regulations changing or recruitment under remote conditions, or other administrative barriers). | The programme has and will mitigate against this (e.g., virtual design, well-connected, integrated into existing services)

The IPE will capture the appropriateness of the service (including fit with professional/service norms) and the feasibility of the implementation, facilitators and barriers to implementation, and implementation strategies.
Likelihood: Low
Impact: High             |
| Unrealistic expectations by funder, programme, and/or partners on ability to detect impact and change  | We will mitigate this through: 
 
● Clear communication
 
● Strong working relationships
 
● Build-up knowledge to detect impact in future evaluations
 
 Sound design, measures, and understanding of the importance of randomisation
Likelihood: Very low
Impact: Low   |

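### Harms rest on perceived harm reported in the process evaluation; no by-arm harm measure is defined, although both arms complete YP-CORE at baseline and endline

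*Protocol*

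**What the plan says.** The Protocol's Analysis of Harms section accepts that therapy can harm, notes that the subject has had little quantitative study, and then names its source: "Unintended consequences of the intervention, including harms, will be explored in the IPE".

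Table 5 (process evaluation, Design) gives the indicator as "Perceived changes in service and client outcomes including unintended consequences and risks of harm", obtained from logic model workshops, staff interviews and interviews with young people.

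Sample and Recruitment sets out the young-person interviews. They are "Interviews with children and young people after completion of the programme", 40 in number, and on recruitment: "We will recruit by providing information sheets through the British Refugee Council for interviews via an opt-in basis". Sampling is purposive, across one-to-one completers, group attenders, crisis clients and a few who declined the offer. The process evaluation's Aims section says the plan may be modified, for example "by not recruiting young people with particularly vulnerable mental health at the end of the intervention". Table 7 (Risks) lists "Staff and young people only want to report positive aspects of the service in IPE evaluation" and rates its likelihood as high.

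On the quantitative side, the Primary outcome measure section schedules YP-CORE at baseline and at three months in both arms and lists safety and harm risk among the outcomes the scale covers. Item 4 reads "I've thought of hurting myself". Primary Analysis compares the total score by arm, by intention to treat, with a two-tailed test.

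**The concern.** The section raises a question of frequency and attribution (does My View make some young people worse?) and assigns it to a source that yields neither a rate nor a comparison. Perceived harm among people who received the programme cannot be separated from what would have happened on the waitlist.

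The young-person interviews are also weakest where harm is most plausible. Nobody who began one-to-one therapy and left is a named sampling group, the most vulnerable may be left out, and the approach is made through the young person's own therapist.

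The trial could therefore report a favourable or null mean effect and no harms identified while a minority deteriorated, or reported self-harm thoughts more often than controls, without any planned analysis that would show it.

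**Working it through.** **1. What the planned by-arm test can see.** Inputs from Table 4 and its text: 145 and 135 participants, R² = 0.5, two-sided alpha 0.05, power 0.8, 6 strata.

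MDES = (t₀.₉₇₅ + t₀.₈₀) × √[(1 − R²) / (P(1 − P)N)]. With P = 145/280 = 0.518, N = 280 and 267 to 272 degrees of freedom, this gives 0.238, which reproduces the stated 0.24. Power at 0.24 SD is 81% in either direction, so average worsening of that size would be detected as readily as improvement.

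**2. What it cannot see.** Suppose a fraction f of the treated arm worsens and the rest are unchanged. The mean moves by f × (individual worsening). For the mean to move by 0.24 SD:
- f = 5%: 0.24 / 0.05 = 4.8 SD each. With the Protocol's illustrative SD of 7.6 this is 36.5 points on a 40-point scale.
- f = 10%: 0.24 / 0.10 = 2.4 SD each, or 18.2 points.

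If the others improve, the mean may even be favourable. The fractions are assumptions; the Protocol gives no harm rate.

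**3. Other planned analyses.**
- The ethics subsection on outcomes worsening before they improve plans, if data allow, to look at change by sessions attended. That is not by arm.
- Exploratory Analysis looks at gains, dose response and selected interactions, not at a deterioration rate.
- The midpoint YP-CORE is used in the evaluation for the treatment group only.
- Nowhere is item 4, or a proportion who worsened, compared by arm.

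**4. What a by-arm table would give.** Half-width of the 95% CI for a risk difference = 1.96 × √[p(1 − p)(1/n₁ + 1/n₂)], at a common rate p:

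| Assumed rate | No loss (145, 135) | Assumed 20% loss (116, 108) |
|---|---|---|
| 10% | 1.96 × √(0.09 × 0.01430) = ±7.0 points | 1.96 × √(0.09 × 0.01788) = ±7.9 points |
| 20% | 1.96 × √(0.16 × 0.01430) = ±9.4 points | 1.96 × √(0.16 × 0.01788) = ±10.5 points |

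The increase detectable with 80% power from a control rate of 10% is about 12 points with no loss and 14 with 20% loss. From 20% it is about 15 and 17. The table would be descriptive for small excesses, but it would give a between-arm estimate where none is now planned.

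**The case against.** Several points on the other side stand.

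- A reader might infer that harm is assessed only through the opt-in interviews with young people. It is not: staff interviews (12 to 16 with therapists and key staff, at two time points) and the workshops also feed the indicator, and therapists see clients who leave. But the same risk-register entry covers staff as well as young people, and neither source supplies a control rate.
- A reader might infer that YP-CORE goes unused for harm. It does not: the total, which includes item 4, is the primary outcome and is tested in both directions. The gap is limited to individual deterioration and item 4 on its own.
- A reader might infer that the interviews are bound to miss harmed young people. The documents do not support that. Leaving out the vulnerable is permitted, not required; crisis clients and some decliners are sampled; and the exact frame is still to be decided. No probability of missing them can properly be calculated, because the sample is purposive and includes crisis clients, whom the Activities section places outside randomisation. Even treating the 40 as random, with an assumed 5% harmed, the chance of interviewing at least one is 1 − 0.95⁴⁰ = 87%. It is 65% if harmed clients opt in half as often and 41% at a quarter as often.
- The harms the section names (stigma, ruptured alliance, disempowerment) are not YP-CORE constructs, and interviews suit them better.
- A by-arm table has its own blind spot. Missing Data drops cases without an endline score, so some early leavers disappear from it too. Therapists also collect YP-CORE unblinded, and growing trust could raise disclosure on item 4 in the treated arm.
- Thresholds and table layouts often sit in a statistical analysis plan, which is not at hand. The Protocol itself, however, fixes the source of harm evidence, and that choice can be questioned here.

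**Conclusion.** The point holds in a limited form. The stated harm source cannot produce a between-arm estimate, its young-person interviews may under-represent early leavers and the most vulnerable, and no by-arm deterioration rate or item 4 comparison is planned although the scores are collected in both arms. Average worsening is covered; worsening in a minority is not.

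The primary estimate is unaffected. What suffers is the weight that a report of no harms identified could bear. The passages above establish the gap without any assumed rate. The precision figures rest on assumed event rates of 10% and 20% and, where stated, an assumed 20% loss. This is a change that should be made, at low cost.

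**What to change.** Keep the process evaluation for harms that YP-CORE does not measure, and add the following.

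1. In Analysis of Harms, a descriptive table by randomised arm, with risk differences and 95% CIs, of (a) the proportion whose YP-CORE total rises from baseline to endline by more than a pre-stated amount and (b) the proportion whose item 4 score rises from baseline. State that a rise is a worsening; the worked example under Sample Size presents a higher treatment mean (20.1 against 18.3) as the effect to be detected.
2. Beside it, the number in each arm with no endline score.
3. In the data transfer, item-level YP-CORE; Data Protection now lists only YP-CORE scores.
4. In Sample and Recruitment, early leavers from therapy as a named sampling group within the existing 40 interviews.

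The cost is one paragraph, one table and a wider data extract, with no new visits, instruments or interviews. The section should state the limits: imprecise proportions, drop-outs without an endline score not captured, and unblinded collection that may raise item 4 disclosure in the treated arm. The figures should be reported as safety estimates, not as further efficacy tests.

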## Sensitivity Analysis

If all high-risk cases are rolled into the treatment group because of the over-ride, we propose to re-run the primary and secondary outcome regressions with high-risk cases excluded to check the effect this has on the impact estimate. In all other respects, the modelling procedure will follow the steps outlined above. Additionally, if the secondary outcome data are skewed, we will check the impact estimate using an ordinal regression model, again using the binary indicator to test the impact effect, controlling for the baseline score and stratum membership.

## Missing Data

We anticipate that the baseline YP CORE questionnaire will be completed by all at the initial assessment interview, given the importance of the baseline in the analysis anyone not completing will be excluded from the analysis. Similarly, we anticipate the questionnaire measures of secondary outcomes to be collected at that same time. The endline primary outcome measures will be collected three months after starting the intervention with attempts

---

made to collect intermediate YP-CORE scores at the 6-week interval (for the treatment group only).

We anticipate that the key risks to missing data will arise with the endline outcome score. Cases without an endline score will not be imputed and will be dropped from the analysis, which will be run using complete case response data only. BRC routinely attempt to collect YP-CORE data after the first six weeks but only for the treatment group. Consequently, we cannot treat both groups equally with respect to missing endline data, so will not attempt to use the 6-weekly score for imputation purposes.

If there is evidence of differential attrition between the treatment and control groups in terms of socio-demographic characteristics, we will construct a weight to account for differential attrition and include a weighted version of the primary and secondary outcomes in the sensitivity analysis to check on the stability of the impact estimate.

If there is no evidence of differential attrition, no weighting will be undertaken.

It is possible, however considered highly unlikely, that young people may give partial responses to the baseline and/or outcome data and, if this occurs, item responses may be imputed to enable a more complete summary score.

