## Design

Table 3: RCT design details

|   |                                |  |
|---|--------------------------------|--|
| Trial type and number of arms            |                                | Non-blinded parallel two-armed randomised control trial with UASC individually randomised to a treatment or waitlist control group (on rolling basis)  |
| Unit of randomisation                    |                                | Young person   |
| Stratification variables (if applicable) |                                | Overall, 6 strata will be used, comprising of one high-risk stratum and five moderate risk strata defined by the British Refugee Council locations, which include four with physical geographical boundaries and a fifth with virtual boundaries. Allocation rates are 50 : 50 for UASCs in moderate risk strata and 66: 34 in high risk strata. |
| Primary outcome                          | Variable                       | Continuous variable – scores ranging from 0 to 40  |
|   | Measure (instrument, scale)    | Mean intervention group YP-CORE score compared to mean control group YP-CORE score collected at endline (3 months from start of intervention) by delivery staff i.e. therapists  |
| Secondary outcome(s)                     | Variable(s)                    | Continuous variable – scores ranging from 7 to 35  |
|   | Measure(s) (instrument, scale) | Mean intervention group SWEMWBS score compared to mean control group SWEMWBS score collected at endline (3 months from start of intervention) by delivery staff i.e. therapists  |

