## Randomisation

Young people will be allocated to their trial arm status after their eligibility check but before their initial assessment (see Figures 2 and 3, above). A random stratified allocation

[figure not shown]
 <https://www.corc.uk.net/outcome-experience-measures/core-measurement-tools/>

 <https://www.corc.uk.net/outcome-experience-measures/short-warwick-edinburgh-mental-wellbeing-scale-swemws/>

procedure will be used. Random numbers will be generated separately for each stratum allowing UASCs to be assigned to treatment as they enter the study, using the random number function within the R statistical programming software package. Different random number seeds will be used for each stratum and we propose to generate blocks of random numbers of size 6, i.e. 3 in the treatment arm and 3 in the control arm. This procedure will reduce the risk of randomly generated long run sequences of allocation to any one of the groups, potentially upsetting the balance between numbers in the treatment and control groups. The random number allocation will generate the allocation lists with a 50 : 50 probability of assignment to treatment and control for moderate-risk strata.

For high risk strata, a probabilistic allocation rate of 0.64 will be assigned to treatment group, with a corresponding probability of 0.36 to the control group. This higher probability of assignment to treatment group for high-risk cases has been requested by BRC to ensure fewer high-risk cases are held back from receiving the treatment than are moderate risk cases. In addition, BRC retain the right of over-riding allocation to group for cases deemed to necessitate immediate treatment. It is possible that some of the high-risk cases identified at referral could be converted to low-risk after initial assessment. Similarly, some cases initially identified as moderate risk could be converted to high-risk. Young people will remain allocated to their strata and analysis will treat them as intention-to-treat on the basis of their original allocation. The implications of the override are further discussed below under the sensitivity analysis.

Figure 5: CONSORT diagram

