## Outcome Measures

### Primary outcome measure

The primary outcome measurement is the Young Person's Clinical Outcomes in Routine Evaluation (YP-CORE) measure. The YP-CORE is a measure of psychological distress and is widely used in mental health and school counselling services. It is freely available to use.

The baseline YP-CORE measurement will take place at the pre-assessment session for young people randomised i.e. both the treatment and control groups. Data will then be collected at the following timepoints:

- Treatment group:
  - Baseline at the pre-assessment session
  - After six My View sessions (midpoint)
  - After three months of My View (endline / post-treatment)
- Waitlist control group:
  - Baseline at the pre-assessment session
  - After three months of being on the waitlist (endline) – this will be at a second pre-assessment session before the young person starts My View
  - After six My View sessions (standard practice, not included in the evaluation)
  - After three months of My View (standard practice, not included in the evaluation).

---

 We have used 47 cases per block as an approximation to the 280 total required (i.e.  $47 \times 6 = 282$ ).

 <https://www.ncbi.nlm.nih.gov/pmc/articles/PMC6860299/>

 <https://www.corc.uk.net/outcome-experience-measures/core-measurement-tools/>

 If, for any reason, the midpoint questionnaire (after 6 sessions) gets delayed and therefore becomes close to the endline questionnaire (to be completed after three months), therapists may decide to only collect the endline.

The measure is brief, with just 10 items covering anxiety, depression, trauma, physical problems, functioning and risk to self. As such, this covers the following short-term outcomes included in the programme's theory of change:

- Psychological and emotional well-being
- Emotional self-regulation
- Safety and risk of harm

For each item, the respondent selects one response to indicate how they have been feeling over the last week:

- Not at all
- Only occasionally
- Sometimes
- Often
- Most or all of the time

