There is the potential to increase the statistical power of the analysis further by including other predictor variables in the regression model. However, calculation of the standardised effect size will use the conditional total variance of the impact effect in its calculation. Using a minimum specification for the model means that the standardised effect size will only be conditioned on the baseline measure and the design variables. Consequently, the effect size

can be used in a meta-analysis study without concerns over comparability caused from effect sizes adjusting for different variables across different studies.

The impact estimator will be calculated using an intention to treat (ITT) analysis to maintain the integrity of randomisation in the allocation stage. This is the fundamental test of the success of the impact effect for this study. This ITT average treatment effect (ATE), however, is based on an ‘offer to treat’. In some circumstances, especially voluntary schemes, it is possible that some people offered the treatment do not participate in the treatment (non-compliers). In such cases, the ITT effect is diminished by those who have not participated. We can calculate the size of the impact effect on those who have participated using formula (2) below, which will be greater than or equal to the ITT average effect. It is also possible that some people in the control group actually receive treatment. This cross over is likely to happen in this particular study because of the over-ride option for young people in the high-risk stratum. In this case, the control group is contaminated by treatment, lowering the ITT estimate of the average treatment effect. Formula (3) below shows how we will adjust for this circumstance of dual cross overs, where the local average treatment effect is calculated as a weighted average of treatment compliers across the treatment and control groups.

in order to adjust for the presence of non-compliers in the treatment group, and assuming we can collect outcome scores for these people, we will also calculate the treatment on the treated, following equation 8 in Bloom (2006), as:

$$TT = \frac{\bar{Y}_t - \bar{Y}_c}{\bar{D}|Z=1} \quad (2)$$

Where the denominator is the proportion receiving treatment in the treatment group

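### Excluding young people without a baseline YP-CORE is an avoidable post-randomisation exclusion, at odds with the intention-to-treat aim; the precision cost is small, and bias is possible but of unknown size

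*Protocol*

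**What the plan says.** Four parts of the protocol bear on this.

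- **Order of events.** Randomisation: "Young people will be allocated to their trial arm status after their eligibility check but before their initial assessment". Primary outcome measure: "The baseline YP-CORE measurement will take place at the pre-assessment session for young people randomised". The Missing Data section places the baseline at the initial assessment interview.
- **Blinding.** Table 3 (Design) describes a "Non-blinded parallel two-armed randomised control trial". Therapists collect the measure.
- **Analysis population.** Primary Analysis states that the estimator is "calculated using an intention to treat (ITT) analysis to maintain the integrity of randomisation", and the Randomisation section says that analysis follows the original allocation. In the regression the endline YP-CORE is the outcome; the baseline score is a covariate beside the stratum indicators.
- **Missing baseline.** Missing Data: "We anticipate that the baseline YP CORE questionnaire will be completed by all at the initial assessment interview", and then, because the baseline matters to the analysis, "anyone not completing will be excluded from the analysis". Partially completed questionnaires may have items imputed. Nothing retains a young person whose baseline is wholly missing, even if an endline score exists.

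**The concern.** Because the baseline follows an open allocation, whether it exists can depend on the arm. A young person told of a three-month wait may be less ready to attend or to complete a questionnaire than one about to start therapy, and the therapist may know which applies. Selecting the analysis set on such an event means that the arms compared are no longer those that randomisation created.

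The exclusion also buys nothing that the model needs. A participant with an endline score and no baseline still carries information on the primary outcome. Such cases can occur: a control's endline is taken at a second pre-assessment session, so a missed first questionnaire does not rule out an endline.

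Two things are at stake: some precision, and possible bias in the primary estimate.

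**Working it through.** **1. The plan's own figure.** Inputs from Table 4 and its text: N = 280 (145 and 135), R² = 0.5, two-sided alpha 0.05, power 0.80, 6 strata. For blocked individual randomisation,

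MDES = (t₀.₉₇₅ + t₀.₈₀) × √[(1 − R²) / (P(1 − P)N)], with df = N − 8.

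With P = 145/280 this gives 0.238, which agrees with the stated 0.24. The figure counts all 280 as analysed.

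**2. Precision: exclusion against retention.** The missing-baseline proportion m is an assumption throughout. Exclusion reduces N to 280(1 − m). Retention keeps N = 280 but, if the baseline is uninformative for those missing it, lowers the effective R² to 0.5(1 − m).

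| m | N if excluded | MDES excluded | MDES retained |
|---|---|---|---|
| 5% | 266 | 0.244 | 0.244 |
| 10% | 252 | 0.251 | 0.249 |
| 15% | 238 | 0.258 | 0.255 |
| 20% | 224 | 0.266 | 0.261 |
| 30% | 196 | 0.285 | 0.271 |

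The recoverable amount is the gap between the last two columns, and it assumes that every excluded case has an endline. It is about 0.002 at 10%.

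**3. Bias.** Simulations used no true effect, 145 and 135 participants, baseline-endline correlation 0.71, SD 7.6 and all endlines observed; strata were left out. Missingness in the first table depends, in controls, on a mix of baseline and endline distress and is commoner in the less distressed. The percentages apply at average distress. Entries are bias in YP-CORE points; negative values favour the intervention.

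| Assumed missing (treatment, control) | Exclude | Pooled-mean imputation | Multiple imputation (endline, arm) | Unadjusted, all with endline |
|---|---|---|---|---|
| 10%, 10%, at random | −0.01 | −0.01 | −0.01 | 0.01 |
| 5%, 15% | −0.34 | +0.71 | +0.25 | 0.00 |
| 5%, 20% | −0.43 | +0.86 | +0.31 | 0.01 |

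In SD units exclusion gives 0.34/7.6 = 0.045 and 0.43/7.6 = 0.057. Against the protocol's illustrative 1.8 points, these are 19% and 24%.

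The result depends on what drives missingness. With 5% and about 15% missing:

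- If missingness follows arm and baseline distress only, exclusion is unbiased (−0.001 SD), because the model conditions on both. Pooled-mean imputation gave +0.058 SD.
- If missingness follows endline distress, exclusion gave −0.047 SD in one set of runs and about −0.07 SD in another. Multiple imputation using endline and arm was unbiased.

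The range for exclusion is therefore nil to about 0.07 SD, or 0.07 × 7.6 = 0.53 points. The unadjusted comparison of everyone with an endline stayed unbiased throughout, at a cost in precision: a standard error of about 0.9 against 0.68 points.

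**The case against.** The case for leaving the rule alone has real substance.

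- **Baselines are expected from everyone.** The protocol sees the main missing-data risk at endline and allows item imputation for partial responses, so the rule mostly touches wholly missing baselines. This stands, and it limits the likely size. It also means that changing the rule costs little.
- **Few excluded cases may be recoverable.** Someone who never attends the first session will seldom have an endline. This stands too; the number cannot be estimated from the protocol. Passing the initial assessment is also listed as an eligibility criterion, so non-attenders were never confirmed eligible. But that criterion is itself applied after allocation, and it is not the same as completing a questionnaire.
- **Intention to treat here means analysis as allocated, with complete cases openly declared.** This is fair as far as it goes. A reader might infer that the plan abandons intention to treat; it does not, since it keeps original allocation despite reclassification, override or non-take-up. The narrower point remains: the exclusion works against the reason given for adopting it.
- **Adjustment protects the estimate.** This is partly right. A reader might multiply a 10-point difference in exclusion rates by a 0.5 SD difference in endline to get (0.15 − 0.05) × 0.5 = 0.05 SD. That describes an unadjusted difference in means. In the planned model, only distress not explained by baseline contributes.
- **The weighted sensitivity analysis covers it.** It does not. It is triggered by socio-demographic differential attrition and returns no excluded case to the primary analysis.

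**Conclusion.** The point holds in a limited form. The rule is a stated post-randomisation exclusion, in an unblinded trial, on a variable that the model uses only for adjustment. It should be changed, but nothing in the protocol shows that it will distort the result.

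On precision, a reader might set 0.238 at N = 280 against 0.258 at N = 238 and conclude that 0.020 is at stake. That compares exclusion with complete baselines. Against retention, the difference at 15% missing is 0.258 − 0.255 = 0.003.

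On bias, the range of nil to about 0.07 SD rests on assumed missingness of 5% and about 15%, and on an assumed link to distress. At the upper end it is 0.07/0.24, or about three tenths of the stated MDES. If non-completion is equal and random it vanishes. The direction favouring the intervention follows from assuming that less distressed controls are the ones missing; the documents do not establish that direction.

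**What to change.** Replace the exclusion sentence in Missing Data with a rule on these lines: every randomised young person with an endline score is analysed in the arm originally allocated; a missing baseline is multiply imputed, with endline score, arm and stratum in the imputation model. Apply the same rule to SWEMWBS.

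Add three items:

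1. Baseline missingness reported by arm.
2. A sensitivity analysis comparing the arms in everyone with an endline, adjusted for stratum but not baseline.
3. The complete-baseline model as a second sensitivity analysis.

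Pooled-mean imputation should not be the primary method, because missingness may depend on arm here and the method can then be more biased than exclusion.

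The cost is a few sentences and a little more analysis work. The imputation assumes that baselines are missing at random given endline, arm and stratum. If missingness instead follows the unseen baseline itself, multiple imputation is biased and the complete-baseline model does better, so both sensitivity analyses are needed. None of this recovers young people without an endline. The order of allocation and the eligibility criterion of passing the initial assessment should be reconciled separately.
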